4.4.2 Exclusion Criteria

- None

4.4.3 Population size of the study and statistical power

According to the records of the Haematology Unit of IRCCS AOU of Bologna, from January 2022 to December 2022, 250 patients with underlying B cell malignancies have been diagnosed with SARS-CoV2 infection and we estimate that approximately 30% had viral shedding longer than 21 days. Thus, we deem that at the end of the study period, approximately 500 patients will be enrolled from IRCCS AOU of Bologna of which about 150 with prolonged infection. Considering the epidemiology of the other participating centers, we expect to reach an overall cohort of about 1000 immunocompromised patients with SARS-CoV-2 infection, with approximately 300 prolonged infections.

Power analysis carried out using Stata v.17.0 showed that a sample size of 1,000 allows to obtain power=80% and alpha=0.05 for a log-rank test comparing 120-days mortality, with a 300/700 allocation ratio, when the difference in mortality rates is at least 4% and mortality rate in the non-persistent COVID is as low as 3%, or when the difference in mortality rates is at least 5% and mortality rate in the non-persistent COVID is at least 4%.

Estimated sample sizes for two-sample comparison of survivor functions
 Log-rank test, Freedman method
 H0: HR = 1 versus Ha: HR != 1

alpha	power	N	N1	N2	nratio	E	delta	hratio	s1	s2	Pr_E
.05	.8	897	627	270	.43	59	2.054	2.054	.95	.9	.06503
.05	.8	1,343	939	404	.43	84	1.839	1.839	.95	.91	.06203
.05	.8	2,282	1,596	686	.43	135	1.626	1.626	.95	.92	.05902
.05	.8	4,900	3,426	1,474	.43	275	1.415	1.415	.95	.93	.05601
.05	.8	18662	13050	5,612	.43	990	1.206	1.206	.95	.94	.05301
.05	.843	.	1	1	.95	.95	.
.05	.8	561	392	169	.43	33	2.581	2.581	.96	.9	.05804
.05	.8	768	537	231	.43	43	2.31	2.31	.96	.91	.05503
.05	.8	1,140	797	343	.43	60	2.043	2.043	.96	.92	.05203

	.05	.8	1,918	1,341	577	.43	94	1.778	1.778	.96	.93	.04902	
	.05	.8	4,070	2,846	1,224	.43	188	1.516	1.516	.96	.94	.04601	
	.05	.8	15304	10702	4,602	.43	659	1.257	1.257	.96	.95	.04301	
	.05	.8	367	256	111	.43	19	3.459	3.459	.97	.9	.05105	
	.05	.8	471	329	142	.43	23	3.096	3.096	.97	.91	.04804	
	.05	.8	638	446	192	.43	29	2.737	2.737	.97	.92	.04503	
	.05	.8	933	652	281	.43	40	2.383	2.383	.97	.93	.04203	
	.05	.8	1,545	1,080	465	.43	61	2.031	2.031	.97	.94	.03902	
	.05	.8	3,221	2,252	969	.43	116	1.684	1.684	.97	.95	.03601	

s1, s2 = survival rates in groups 1 and 2
 N1, N2 = sample size required in groups 1 and 2.

As regards the analysis on prevalence of imaging alterations, due to the larger expected difference between the two groups, the population size of 1,000 is completely adequate.

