2.1 Background and rationale

Although the impact of COVID-19 has been significantly reduced thanks to the effectiveness of vaccination and antiviral treatments, the risk of breakthrough infection remains higher in the immunocompromised population [1].

Immunocompromised patients are at increased risk for SARS-CoV-2-associated morbidity and mortality due to immunologic deficits that limit normal immune response and viral clearance [2-3]. Furthermore, the type of immunosuppression and the treatments performed significantly impact the natural trajectory of the COVID-19 infection, as in the case of patients with impaired adaptive humoral immunity who are relatively protected from acute infectious toxicity but have a high risk of prolonged viral shedding, viral rebound, and chronic infection [2-3].

In this group of patients, also known as “long persisters”, we find especially haematological patients with B cell malignancies or undergoing B cell targeting therapies such as anti-CD20 and CAR-T cell therapy. These patients, in addition to the complications related to SARS-CoV-2 infection itself, represent a particularly interesting population as the lack of viral clearance can lead to delays in life-saving treatments.

Despite major advances in our understanding of COVID-19, there is still a lack of consensus on how to define the condition of persistent infection in immunocompromised patients, also called “protracted SARS-CoV-2 infection” or “persistent inflammatory sero-negative COVID” [4-5]. In particular, two recent studies have tried to distinguish this phenomenon from “long COVID-19” and “post-COVID-19 condition”, which is defined by the WHO as a syndrome that occurs in individuals who have contracted COVID-19 in the previous 3 months and have at least 2 months of ongoing symptoms (such as fatigue, dyspnoea, and cognitive dysfunction), with no alternative diagnoses [6]. Both studies [4-5] suggest the use of diagnostic criteria that combine baseline host immunodeficiency, clinical signs and virological data, which we can summarize as follows:

- Host criterion: underlying immunosuppression such as HCT, CAR T-cell recipient, lymphoma or B-cell malignancy, SOT, Anti-CD20 therapy or other B/T cell targeted therapies, primary and acquired immunodeficiencies.
- Clinical criterion: persistent/relapsing symptoms (fever, dyspnea, hypoxemia) and/or persistent/relapsing changes on chest-X ray or CT scan after extensive negative infectious work up.

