3.3 Endpoints

The first primary endpoint variable will be the prevalence of persisting SARS-CoV-2 infection among the immunocompromised patients defined as the persistence or the recurrence of symptoms and signs (fever, dyspnea, hypoxemia, changes on chest-X ray or CT scan) and positive SARS-CoV-2 PCR ≥ 21 days after the time 0 (day of the first test positive for SARS-CoV2 infection).

The endpoints for the secondary objectives are:

- Duration of treatment carried out to address the persistent COVID-19 condition and treatment-related adverse effects.
- Duration of viral shedding, defined as the number of days between the first positive test and first negative PCR test.
- Duration of symptoms, defined as the number of days between symptoms onset and the clinical cure.
- Prevalence of imaging alterations, defined as the presence of new ground-glass and/or crazy paving and/or interstitial infiltrates at chest CT scan during the persisting infection (starting from 21 days after the first positive test until viral clearance).
- Re-infection within 120 days, define as new positive test with or without symptoms after viral clearance has been achieved.
- All-cause 120-day mortality.

4. Investigational plan

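### The 300 persisters and 300/700 split in 4.4.3 rest on viral shedding alone, but the 3.3 endpoint also needs symptoms or signs, so the number meeting the endpoint is not established

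*Combined protocol and SAP*

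**What the plan says.** Section 4.4.3 starts from 250 infected patients seen at the coordinating centre in 2022, of whom "we estimate that approximately 30% had viral shedding longer than 21 days". The same 30% gives 150 prolonged infections among 500 patients at that centre and 300 among 1,000 overall. The power statement is that "a sample size of 1,000 allows to obtain power=80% and alpha=0.05 for a log-rank test comparing 120-days mortality", "with a 300/700 allocation ratio", for mortality of 3% vs 7%, or for a 5-point difference when comparator mortality is at least 4%.

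Section 3.3 defines the primary endpoint differently: "persistence or the recurrence of symptoms and signs (fever, dyspnea, hypoxemia, changes on chest-X ray or CT scan) and positive SARS-CoV-2 PCR" at 21 days or more after the first positive test. Duration of viral shedding is a separate secondary endpoint in 3.3, defined by PCR results only.

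Section 4.8 compares two groups, persistent and non-persistent, and uses all enrolled patients as the denominator for prevalence. No section says where a patient belongs who is still PCR-positive at day 21 without symptoms or signs.

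**The concern.** The planning count and the endpoint describe different conditions. Shedding beyond 21 days is only one of the two components that 3.3 requires, yet 4.4.3 uses it as the count of persisters.

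Section 2.1 gives a reason to think the two may diverge in this population. It describes patients with impaired humoral immunity as "relatively protected from acute infectious toxicity but have a high risk of prolonged viral shedding, viral rebound, and chronic infection". That makes long shedding without qualifying signs plausible, though it does not say how common it is.

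Two things are at stake:

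- The stated power for 120-day mortality depends on an allocation that has not been estimated for the defined endpoint.
- Long shedders without symptoms or imaging signs sit in the comparator beside patients who cleared the virus. This affects how the risk-factor and outcome contrasts are read, and in particular the comparison of shedding duration.

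**Working it through.** **Inputs.** From the 4.4.3 output: "Log-rank test, Freedman method"; two-sided test ("H0: HR = 1 versus Ha: HR != 1"); alpha 0.05; power 80%; allocation ratio k = 0.43; survival .97/.93 (3% vs 7% mortality) and .96/.91 (4% vs 9%). Total N = 1,000. Normal quantiles are 1.960 and 0.842. The share of long shedders who meet the full 3.3 definition is not given, so it is an assumption shown as a range.

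**Step 1: reproduce the plan's rows.**

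- HR = ln(s2)/ln(s1)
- E = (1.960 + 0.842)² (1 + k·HR)² / [k (HR − 1)²]
- Pr_E = [(1 − s1) + k(1 − s2)] / (1 + k)
- N = E / Pr_E

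For 3% vs 7%: HR = 2.383, E = 39.1, Pr_E = (0.03 + 0.43 × 0.07)/1.43 = 0.0420, N = 932 after rounding up (plan: 933). For 4% vs 9%: HR = 2.310, E = 42.2, Pr_E = 0.0550, N = 768 (plan: 768). The plan's arithmetic is right; the question is the input.

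**Step 2: power at N = 1,000 with fewer persisters, mortality rates held fixed.** Let n be the number of persisters, k = n/(1,000 − n), m1 and m2 the comparator and persister mortality, and E = (1,000 − n)·m1 + n·m2. Then

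power = Φ[ √(E·k) (HR − 1)/(1 + k·HR) − 1.960 ].

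Worked for 3% vs 7%:

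- n = 300: k = 0.429, E = 42.0, first term 2.902, power Φ(0.942) = 82.7%.
- n = 150: k = 0.176, E = 36.0, first term 2.453, power Φ(0.493) = 68.9%.

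If all persisters come from the 300 long shedders, the remaining long shedders form (300 − n)/(1,000 − n) of the comparator.

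| Persisters n | Share of 300 | Long shedders in comparator | Power, 3% vs 7% | Power, 4% vs 9% |
|---|---|---|---|---|
| 300 | 100% | 0% | 82.7% | 89.2% |
| 245 | 82% | 7.3% | 80.0% | 86.9% |
| 240 | 80% | 7.9% | 79.7% | 86.6% |
| 170 | 57% | 15.7% | 72.3% | 80.0% |
| 150 | 50% | 17.6% | 68.9% | 76.9% |
| 90 | 30% | 23.1% | 53.2% | 60.9% |

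The smallest n that keeps 80% power is 245 for 3% vs 7% and 170 for 4% vs 9%.

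**Step 3: relax the fixed mortality rates.** Both scenarios below are assumptions. Each keeps the 700 other patients at 3% and the 300 long shedders at 7% on average.

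- *Long shedders without signs die at the persister rate (7%).* Comparator mortality at n = 240 is (700 × 0.03 + 60 × 0.07)/760 = 3.32%, and power is 70.5%. At n = 150 it is (21 + 10.5)/850 = 3.71%, and power is 46.6%.
- *Long shedders without signs die at the comparator rate (3%).* Persister mortality at n = 240 is (21 − 60 × 0.03)/240 = 8.0%, and power is about 92%. At n = 150 it is (21 − 4.5)/150 = 11.0%, and power exceeds 99%.

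For 4% vs 9%, the same two scenarios give 78.6% and about 96% at n = 240, and 54.3% and over 99% at n = 150.

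**The case against.** Several counter-arguments have force.

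- **The direction of the power change is not fixed.** Restricting the exposed group to patients with fever, dyspnoea, hypoxaemia or imaging changes could raise its mortality, and Step 3 shows that power can then rise. A reader might infer from the Step 2 table that power is lost. The documents do not support this without the fixed-mortality condition. This stands.
- **300 is not a ceiling.** A reader might take it as an upper limit for the endpoint. But 3.3 ends shedding at the first negative PCR while its primary endpoint admits recurrence, and 2.1 names viral rebound as a risk. A patient who turned negative before day 21 and then relapsed could count as a persister without being among the 30%. This stands: below 300 is probable, not certain.
- **The excluded group is not simply the symptom-free.** Imaging changes count as signs, so a patient without symptoms may still qualify. Section 2.1 speaks of protection from acute toxicity, not of absent signs at day 21. This stands.
- **The comparator is as defined.** Under a deliberately combined clinical and virological definition, long shedders without signs are correctly non-cases. Calling the contrasts diluted presupposes a virological target. This largely stands. It supports keeping the 3.3 definition as primary and treating the middle group in a sensitivity analysis.
- **The reach is limited.** Mortality is a secondary endpoint, and the prevalence estimate does not depend on a 300/700 split. At a share near 80%, power for 3% vs 7% is still about 80%. This stands, and it limits the severity.

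Section 2.1 also says the 21-day reference will be used to identify persistent infection. Read as PCR alone, that would conflict with 3.3, so it does not settle the matter. None of these arguments reconciles 4.4.3 with 3.3.

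**Conclusion.** The mismatch is explicit and unresolved: the stated power rests on a count for a condition other than the endpoint. The number of patients meeting 3.3 is unknown and probably below 300. The claim of 80% power at 3% vs 7% survives only if at least about 82% of the expected long shedders meet the full definition; at 4% vs 9% the threshold is about 57%. Both thresholds assume N = 1,000, the Freedman method, unchanged mortality rates and no persisters from outside the 300. Confidence is high for the mismatch. It is low for the size and direction of any power change, because the documents give neither the share nor the mortality of long shedders without signs. The point should be corrected before analysis, but it does not invalidate the prevalence objective.

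**What to change.** **In 4.4.3:** label the 30% and the 300 as shedding-based figures. Give the expected number meeting the 3.3 definition as a range, if possible from the 250 coordinating-centre records behind the 30%. Restate the allocation and the detectable difference for that range, and state the mortality assumed for each group.

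**In 4.8:** keep the 3.3 definition as primary. Tabulate four categories:

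1. cleared before day 21;
2. PCR-positive at or after day 21 without symptoms or signs;
3. persisting infection as defined in 3.3;
4. day-21 PCR status unknown.

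Add a sensitivity analysis that repeats the persister comparison with the second category removed from the comparator.

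**Cost:** restated planning figures, one table and one extra analysis, with no additional patients. The stated detectable difference may become less favourable. Under 4.3, screening for persisting infection follows routine practice, so some patients, particularly those without symptoms, may not have been retested around day 21 and will be unclassifiable. The fourth category is there to show how many.

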4.4.1 Inclusion Criteria

- Diagnosis of B cell malignancies or previous treatment with B cell targeting therapies.
- Diagnosis of proven SARS-CoV-2 infection confirmed by a PCR test (only the first infection during the study period will be considered, re-infection will be counted as a secondary endpoint).
- Provision of signed and dated informed consent.

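### The 80% power claim for a 5-point mortality difference sets a floor on baseline mortality where it needs a ceiling; by the plan's own formula it fails above about 5.8%

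*Combined protocol and SAP*

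**What the plan says.** Section 4.4.3 expects about 1,000 patients, of whom about 300 have prolonged infection. It claims "power=80% and alpha=0.05 for a log-rank test comparing 120-days mortality" at a 300/700 split in either of two situations. The first is a difference of at least 4 points with non-persistent mortality as low as 3%. The second is "when the difference in mortality rates is at least 5% and mortality rate in the non-persistent COVID is at least 4" per cent.

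A Stata table follows, headed "Log-rank test, Freedman method", with a two-sided hypothesis ("H0: HR = 1 versus Ha: HR != 1") and an allocation ratio of 0.43. Its baselines (s1) are survival of 0.97, 0.96 and 0.95, that is, mortality of 3%, 4% and 5%.

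The figure of 300 comes from the coordinating centre's records for 2022, about which the plan says "we estimate that approximately 30% had viral shedding longer than 21 days". Section 3.3 defines persistence more narrowly: a positive PCR at 21 days or later, together with a clinical component "defined as the persistence or the recurrence of symptoms and signs (fever, dyspnea, hypoxemia, changes on chest-X ray or CT scan"). For imaging, section 4.4.3 says only that "the population size of 1,000 is completely adequate".

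**The concern.** For a fixed absolute difference, raising the baseline moves the hazard ratio towards 1. Events increase, but not enough to compensate, so power falls. A valid power statement of this kind therefore needs a ceiling on the baseline. The sentence gives a floor instead, which extends the claim to every baseline above 4%.

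The documents state no expected 120-day mortality for this cohort, so a reader cannot tell whether the true baseline lies where the claim is valid. Someone who expects 8% or 10% would take from the sentence that a 5-point difference is covered at 80% power. A non-significant comparison could then be given more weight than it deserves.

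A second uncertainty bears on the same calculation. The 300 persisters are counted on duration of shedding alone, whereas section 3.3 also requires symptoms or signs.

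**Working it through.** **Inputs (section 4.4.3).** Two-sided alpha 0.05; power 80%; Freedman log-rank; ratio r = 0.43 (persistent to non-persistent); cohort 700 + 300. The plan states no allowance for loss to follow-up and none is used here.

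**Formulas.** With survival s1 (non-persistent) and s2 (persistent):

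- HR = ln(s2)/ln(s1)
- E = (1.960 + 0.842)² × (1 + r·HR)² / [r·(HR − 1)²]
- Pr_E = [(1 − s1) + r·(1 − s2)] / (1 + r)
- N = E / Pr_E

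**Reproducing the table.** For 5% against 10%: HR = ln(0.90)/ln(0.95) = 2.054; E = 58.27; Pr_E = 0.06503; N = 895.9, against 897 printed. The other two 5-point rows give 767.7 (printed 768) and 636.4 (printed 638). All 17 evaluable rows agree within 2 patients, so this is the formula the plan used.

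**Extending it.** For 6% against 11%: HR = 1.883, E = 76.62, N = 1,021. N equals 1,000 at a baseline of 5.83%.

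**Power at 700/300.** Power = Φ{√(E·φ)·(HR − 1)/(1 + φ·HR) − 1.96}, where E is now the expected number of deaths, 700(1 − s1) + 300(1 − s2), and φ = 300/700. For 8% against 13%: E = 56 + 39 = 95, HR = 1.670, and the argument is 2.492 − 1.960 = 0.532, which gives 70.3%.

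The simulated column is a two-sided log-rank test with exponential survival, censoring at day 120, no loss to follow-up and 20,000 replicates per point (standard error about 0.3 points).

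| Baseline, 5-point difference | N for 80% (Freedman) | Power at 700/300 (Freedman) | Power, simulated log-rank |
|---|---|---|---|
| 4% | 768 (printed) | 89.2% | 86.9% |
| 5% | 897 (printed) | 84.1% | 81.8% |
| 6% | 1,021 | 79.1% | 77.0% |
| 7% | 1,143 | 74.5% | not run |
| 8% | 1,262 | 70.3% | 68.7% |
| 10% | 1,492 | 63.0% | 62.2% |

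**Dependence on method.** The baseline at which 5-point power equals 80% is 5.82% by Freedman at exactly 700/300, 5.16% by a pooled two-proportion test and 4.21% by Schoenfeld. The simulation puts it between 5% and 6%.

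**Width of the overstatement.** By Freedman, the difference detectable with 80% power is 5.06, 5.67 and 6.18 points at baselines of 6%, 8% and 10%. By pooled proportions it is 5.30, 5.91 and 6.42 points.

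**The 4-point clause.** If its baseline is also read as a floor, the printed rows contradict it without any extrapolation: 933 patients at 3%, but 1,140 at 4% and 1,343 at 5%. Freedman power at 700/300 is 82.7% at 3% and 74.7% at 4%, crossing 80% at about 3.3%. The simulated figure for 3% against 7% is 79.7%.

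**Number of persisters.** The documents give no share of long shedders with symptoms or signs, so 150 to 300 is an assumed range. Freedman power in a cohort of 1,000:

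| Persisters | 3% vs 7% | 4% vs 9% | 5% vs 10% |
|---|---|---|---|
| 300 | 82.7% | 89.2% | 84.1% |
| 240 | 79.7% | 86.6% | 80.8% |
| 180 | 73.7% | 81.4% | 74.4% |
| 150 | 68.9% | 76.9% | 69.3% |

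Power of 80% needs about 245, 170 and 231 persisters respectively.

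**The case against.** The best defence is that the sentence summarises the table printed directly beneath it. At the two baselines it could mean, 4% and 5%, the requirement is 768 and 897, both under 1,000, and no printed row contradicts the 5-point clause. The failure appears only on extrapolation, is under one point of power at 6%, and becomes material only at baselines the documents nowhere predict. Mortality is a secondary endpoint in an observational study, and the 1,000 comes from expected accrual, not from this calculation. Correcting the sentence changes no enrolment and no analysis.

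Most of this is fair and limits how serious the point is. It does not rescue the wording. A reader is told that the condition is a minimum, when the direction of the table shows that it should be a maximum.

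Two narrower objections also have force. Schoenfeld's 4.2% should carry little weight: it implies 75.8% power at a 5% baseline, where the simulation gives 81.8%. The persister count is a separate matter and cannot be called a firm bound. Adding a clinical requirement probably lowers the count. But a relapse after an early negative PCR might qualify under section 3.3, and section 4.4.1 admits patients by "Diagnosis of B cell malignancies or previous treatment with B cell targeting therapies", a wider group than the B cell malignancy records behind the 30%. The main conclusion does not depend on either.

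**Conclusion.** The concern holds. As written, the 5-point claim is true at the tabulated baselines of 4% and 5% and false above about 5.8% by the plan's own method. At 8% and 10% the power for a 5-point difference is about 70% and 63%, not 80%. The ceiling is an extrapolation of the Freedman formula, assuming a 700/300 split and no loss to follow-up. Other methods place it lower, and none of those tried removes it.

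The effect is confined to differences of 5.0 to 5.7 points at a baseline of 8%, and 5.0 to 6.2 points at 10%; larger differences still reach 80%. Because the endpoint is secondary, this should be corrected but does not threaten the study. A persister count below 300 would erode power further, by an amount the documents do not allow one to fix.

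**What to change.** Replace the power sentence in section 4.4.3 with wording such as: by the Freedman method, 1,000 patients (700/300) give at least 80% power for a difference of at least 4 points if non-persistent mortality is at most about 3%, or at least 5 points if it is at most about 5%; at 6%, 8% and 10% the detectable difference is about 5.1, 5.7 and 6.2 points. The first two limits stay within the printed rows.

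Add the 120-day mortality expected in non-persisters, with its source. State that the 300 persisters rest on shedding beyond 21 days alone, and show power over an assumed range of 150 to 300 persisters under the section 3.3 definition.

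The cost is a text change. No further patients or data are needed, but the stated power becomes less favourable.

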4.5 Study duration

The study will be composed by:

- a prospective recruitment period of 1 year after Ethics Committees' approvals and directorates' permissions to conduct the study (during which retrospective data will also be collected);
- Follow-up period of 120-days from the diagnosis of SARS-CoV-2 infection;
- Data collection and analysis, that will last 6 months

For an overall duration of approximately 22 months

